6.7.2 Adverse Events

All AEs recorded on the CRF will be coded using the MedDRA dictionary [Version 23.1 (or a later version if updated during the study)] and treatment – emergent AEs (TEAEs) are defined as follows:

- TEAEs are events with start date on or after the date and time of the first dose of treatment or events with start date prior to the date and time of the first dose of treatment whose severity worsens on or after the date and time of the first dose of treatment.

If an event where AE start/stop date is missing/partial, the following imputation rule will be applied:

Imputation rules for start date of AEs:

- If start date is completely missing, start date will be imputed to be the first dose date of study treatment;
- For a partial start date (day is missing, or day and month are both missing):
 - none missing part of the partial date < the first dose date: the last day of the month/year
 - none missing part of the partial date = the first dose date: the first dose date
 - none missing part of the partial date > the first dose date: the first day of the month/year

Imputation rules for end date of AEs:

CONFIDENTIAL

Page 24 of 30

Statistical Analysis Plan

Sponsor Name: Bridge Biotherapeutics, Inc.
Sponsor Protocol ID: BBT401-UC-005

- If end date is completely missing, then end date remains missing (assuming ongoing event);
- For a partial end date, the last day/month will be imputed. If only day is missing, the last day of the month will be imputed; if both day and month are missing, then the last day of the year will be imputed. If the imputed end date is after the end of study date, then imputed end date will be set as the end of study date.

If imputed AE start date is after the imputed AE stop date, then start date will be set to the imputed AE stop date.

Imputed dates will be used to determine whether an AE is treatment-emergent and will not be displayed in data listings.

All AE data will be listed. Treatment-emergence status will be flagged in the listing. In addition, corresponding listings of SAEs, AEs leading to discontinuation of treatment and AEs resulting in death will be produced.

Summary tables of TEAEs will be produced for each phase by treatment group for the Safety Population. AE starting date which is within the induction phase will be summarised under the induction phase. Similarly, an AE starting date which is within the extension phase will be summarised under the extension phase.

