The severity of all AEs is recorded as mild, moderate, or severe. If severity is missing for a TEAE, it will be considered severe only in the overall category in the summary tables.

The relationship between an AE and treatment is assessed as not related, unlikely related, possible related, or related. A treatment-related AE is an AE considered by the investigator as possibly related, or related to treatment or with unknown/missing relationship to treatment.

An overview table will summarize the number and percentage of subjects with at least one of the following TEAEs, where subjects with more than one TEAE in a particular category are counted only once in that category:

- Any TEAE;
- Treatment-Related TEAE;
- TEAE Leading to Treatment Discontinuation;
- Serious Treatment Emergent Adverse Event (Serious TEAE);
- Treatment-Related Serious TEAE;
- Serious TEAE Leading to Death;
- Treatment-Related Serious TEAE Leading to Death;
- Serious TEAE Leading to Treatment Discontinuation;

Statistical Analysis Plan

Sponsor Name: Bridge Biotherapeutics, Inc.
Sponsor Protocol ID: BBT401-UC-005

- Treatment-Related Serious TEAE Leading to Treatment Discontinuation

The number and percentage of subjects reporting each AE will be summarised by System Organ Class (SOC) and Preferred Term (PT) for each phase and by treatment group for the Safety Population. Tables will be sorted alphabetically by SOC. PTs will be sorted by descending overall total. The following summaries will be produced:

- TEAEs, by SOC and PT;
- Treatment-Related TEAEs, by SOC and PT;
- TEAEs by Relationship to Treatment, by SOC and PT;
- TEAEs by Maximum Severity, by SOC and PT;
- TEAEs Related to Treatment by Maximum Severity, by SOC and PT;
- TEAEs Causing Discontinuation from Treatment, by SOC and PT;
- Treatment-Related TEAEs Causing Discontinuation from Treatment, by SOC and PT;
- Serious TEAEs, by SOC and PT;
- Treatment-Related Serious TEAEs, by SOC and PT;
- TEAEs Leading to Death, by SOC and PT;

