In the above summaries, subjects with more than one AE within a particular SOC are counted only once for that SOC. Similarly, subjects with more than one AE within a particular PT are counted only once for that PT. For summaries by maximum severity, subjects with multiple AEs within a particular SOC or PT will be counted under the category of their most severe AE within that SOC or PT. AEs with missing severity will be included (as severe) in the overall count of subjects with AEs, but will not be included in the counts of subjects with AEs within a SOC or PT.

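### A treatment-emergent adverse event with no severity grade is left out of its SOC and PT counts, so those counts would be too low if any grade is missing

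*SAP*

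**What the plan says.** SAP 6.7.2 states the rule twice. Before the overview table it says: "If severity is missing for a TEAE, it will be considered severe only in the overall category in the summary tables". After the list of SOC/PT summaries it says: "AEs with missing severity will be included (as severe) in the overall count of subjects with AEs", and then "but will not be included in the counts of subjects with AEs within a SOC or PT".

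The second statement closes a paragraph with two scopes. The paragraph opens on all the listed tables: "In the above summaries, subjects with more than one AE within a particular SOC are counted only once for that SOC". The sentence just before the exclusion concerns only part of them: "For summaries by maximum severity, subjects with multiple AEs within a particular SOC or PT will be counted" under their most severe event.

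Ten SOC/PT summaries are listed, and two of them are by maximum severity. The other eight, including all TEAEs, serious TEAEs and TEAEs leading to death, do not use severity.

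The section also expects complete grading: "The severity of all AEs is recorded as mild, moderate, or severe". It keeps every event in the listings: "All AE data will be listed". The protocol has no rule for missing severity.

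**The concern.** An event with a known coded term belongs in the count for that term. A blank severity field does not change which SOC or PT it falls in, yet the rule removes it from both. Elsewhere SAP 6.7.2 treats gaps in the opposite way: a missing relationship counts as treatment-related, and a completely missing start date is set to the first dose date. In both cases the event stays in the tables. The exclusion also conflicts with the same section's undertaking to give the number of subjects reporting each event by SOC and PT.

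Adverse events and serious adverse events are the primary safety endpoints (protocol 2.2.1, SAP 3.1). The SOC/PT tables are where a reader compares arms term by term. With 12 subjects per arm, one subject can decide whether a term appears in an arm at all. Because the scope is unclear, two programmers could also build different tables from the same text.

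**Working it through.** The plan states no figure on this point, so there is none to reproduce. The check applies the rule to a small example and then sizes the effect.

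**Inputs from the documents**
- Arm size: 12 per arm in the induction phase (protocol 3.1, SAP 2.2).
- Counting unit: subjects, once per SOC and once per PT; for PTs, "subjects with more than one AE within a particular PT are counted only once for that PT" (SAP 6.7.2).
- Ungraded events: in the overall row, not in SOC or PT rows (SAP 6.7.2).

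**1. The rule applied to an invented arm of 12.** Subject 1 has mild nausea and mild headache, subject 2 moderate nausea, subject 3 a severe colitis flare, subject 4 ungraded nausea and subject 5 an ungraded respiratory infection. That is 6 TEAEs in 5 subjects, 2 of them ungraded.

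| Row | Rule read literally | Ungraded events kept |
|---|---|---|
| Overall | 5 | 5 |
| SOC gastrointestinal | 3 | 4 |
| SOC nervous system | 1 | 1 |
| SOC infections | no row | 1 |
| PT nausea | 2 | 3 |
| PT headache | 1 | 1 |
| PT colitis flare | 1 | 1 |
| PT respiratory infection | no row | 1 |

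Subjects 4 and 5 are in the overall row and in no SOC or PT row. The respiratory infection disappears from the table.

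**2. Size of one loss.** 1/12 = 8.3 percentage points; nausea falls from 3/12 = 25.0% to 2/12 = 16.7%. Where the lost subject was the only case, exact (Clopper-Pearson) 95% intervals give:
- 1/12 = 8.3% (0.2% to 38.5%)
- 0/12 = 0% (0% to 26.5%)

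A row changes only if the ungraded event is that subject's sole event in it. Had subject 4 also had a graded nausea event, the nausea count would stand.

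**3. Chance that the rule is triggered at all.** The documents give neither the number of TEAEs nor the proportion ungraded. Assume n TEAEs, each ungraded independently with probability m. Then P(at least one ungraded) = 1 − (1 − m)^n.
- n = 20, m = 0.5%: 1 − 0.995^20 = 9.5%
- n = 40, m = 1%: 1 − 0.99^40 = 33%
- n = 80, m = 5%: 1 − 0.95^80 = 98.3%
- m = 0: no effect

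The width of this range reflects the assumptions and is not an estimate for this trial.

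**4. The two readings of scope**
- *Broad.* The first statement refers to summary tables without limiting it to severity tables, and the later paragraph opens on all the listed summaries. All ten tables are affected, including eight where severity plays no part.
- *Narrow.* The exclusion follows directly on the maximum-severity sentence. Two tables are affected. In those, an ungraded event counts as severe overall and is absent by term, so the subject count for a term can be lower than in the main TEAE table.

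A row can lose a subject on either reading; the scope decides only how many tables are affected.

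**The case against.** The strongest case against is that the rule may never operate. Severity is to be recorded for every event, protocol 7.4.1 and Appendix 1 require the investigator to grade it, and protocol Appendix 4 provides for source data verification and query resolution. This stands: the effect is conditional, and a reader who infers that the main tables will under-count as planned goes beyond the text.

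The narrow scope is also arguable. Calling an event severe has a function only where severity categories are displayed, and the sentence follows one about maximum-severity tables. This stands as an ambiguity. It does not remove the point, because the two maximum-severity tables would still omit the event by term.

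Three stronger inferences are not supported:
- *That SOC and PT rows should add up to the overall row.* Subjects are counted once per row and can appear in several. In the example with the ungraded events removed altogether, the SOC rows sum to 3 + 1 = 4 against 3 subjects overall.
- *That every ungraded event costs 8.3 points, or that every SOC and PT line is too low.* Only rows where the ungraded event is a subject's sole event change. The denominator of 12 is for the induction arms; extension groups differ after reassignment.
- *That a serious event could vanish from the report.* All events are listed, with separate listings of serious events, discontinuations and deaths. The overview table has no SOC or PT breakdown, so the exclusion does not reach it.

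**Conclusion.** The concern holds as a conditional and minor one. As written, SAP 6.7.2 would give SOC or PT counts that are too low if any TEAE lacks a grade and that event is the subject's only one in the row. Each subject lost costs 8.3 percentage points in a 12-subject induction arm, and the subject may be left in the overall row with no term. On the broad reading this can reach the main, serious and death tables; on the narrow reading it makes the two maximum-severity tables inconsistent with the main TEAE table. The documents do not settle which reading is meant.

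The 8.3 points assume 12 subjects in the arm. How often the problem would arise is unknown; given the grading and data-checking requirements, missing grades are probably few. The event record itself is intact in the listings.

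**What to change.** Replace the exclusion sentence in SAP 6.7.2, and align the earlier statement with it, to say that missing severity does not affect inclusion in any SOC or PT count. In the two maximum-severity tables, show such events in a missing-severity row at SOC, PT and overall level.

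An alternative is to count them as severe at all three levels. That is consistent too, with the small downside that it may inflate severe counts by term in small arms.

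Either option is a short change of wording plus the matching table shells. It needs no new data and changes no endpoint.

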6.7.3 Laboratory Evaluations

Data for the following hematology, blood chemistry, and urinalysis analytes received recorded in the CRF will be summarised and listed and by visit for each study phase and by treatment group for the Safety Population.

Statistical Analysis Plan

Sponsor Name: Bridge Biotherapeutics, Inc.
 Sponsor Protocol ID: BBT401-UC-005

Hematology	Clinical Chemistry	Urinalysis
Hematocrit	Alanine aminotransferase	Bilirubin
Hemoglobin	Albumin	Blood
Mean cell hemoglobin	Alkaline phosphatase	Colour and appearance
Mean cell hemoglobin concentration	Amylase	Glucose
Mean cell volume	Aspartate aminotransferase	Ketones
Platelet count	Bicarbonate	Leukocyte esterase
Red blood cell count	Blood urea nitrogen	Nitrite
White blood cell (WBC) count	Calcium	pH
WBC differential:	Chloride	Protein
Basophils	Cholesterol	Specific gravity
Eosinophils	Creatine kinase	Urobilinogen
Lymphocytes	Creatinine	Microscopic examination
Monocytes	Direct bilirubin	
Neutrophils	Gamma-glutamyl transferase	Coagulation
	Glucose	Prothrombin time
	Lipase	Activated partial thromboplastin time
	Potassium	International normalised ratio
	Sodium	
	Total bilirubin	
	Total protein	
	Triglycerides	
	Uric acid	

All laboratory data will be reported in International System of Units (SI)/Conventional units. Out-of-reference-range values will be flagged as high (H) or low (L) in the listings.

6.7.4 Vital Signs

The following vital signs will be summarised and listed by visit for each study phase and by treatment group for the Safety Population.

- systolic and diastolic blood pressure (mmHg);
- pulse rate (beats/min);
- tympanic temperature (°C).

6.7.5 12-Lead Electrocardiograms

The following quantitative ECG measurements will be taken during the study:

- heart rate (beats/min);
- PR interval (ms);
- QRS duration (ms);
- QT interval (ms);
- QTcF interval (ms);
- RR interval (ms);

CONFIDENTIAL

Page 27 of 30

Statistical Analysis Plan

Sponsor Name: Bridge Biotherapeutics, Inc.
Sponsor Protocol ID: BBT401-UC-005

An overall Investigator assessment of ECG will be provided (categories "normal", "abnormal, not clinically significant" and "abnormal, clinically significant").

The ECG measurements and investigator assessment will be summarised and be listed by visit for each study phase and by treatment group for the Safety Population.

6.7.6 Physical Examination

Physical examination results (normal/ abnormal, not clinically significant/ abnormal, clinically significant) will be summarised and listed for each subject for each study phase and by treatment group for the Safety Population.

6.8 PK Analysis

Tissue concentrations data for the biopsy samples collected on Day 57 will be summarized and listed by treatment group for the PK population.

6.9 Interim Analysis

No formal interim analyses are planned for this study. However, an assessment of clinical remission will be performed at Day 57 to determine whether a subject will progress into the extension phase and the dose to be administered.

7. Changes in Planned Analysis

- histopathology healing using the Geboes score, as measured by change from baseline**

During the study design stage, it was determined that this study should be as similar as the BBT401-UC-004. Therefore, the same endpoint was kept as it is. During the BBT401-UC-004 CRF design, it was determined that it is difficult to record and compare Geboes Score directly and hence the study team decided to use histologic category as the tool for histopathology.

To be consistent with the BBT401-UC-004, it is decided the way of analysis and the endpoint should be modified accordingly. Therefore, a change in histopathology analysis is amended to be consistent with the BBT401-UC-004.

- Change from baseline to Day 57 in the Total Mayo score**

The study team decided to present the absolute change from baseline to Day 57 in the Total Mayo score.

- Modified Mayo remission rate at Day 57, as defined by a mMCS <=2, RBS=0, mESS<=1, SFS=0 or (1 if at least 1 point drop from baseline)**

The study team decided to summarize the modified Mayo remission rate to better evaluate the effects of BBT-401-1S.

- Symptomatic remission rate at Day 57, as defined by RBS=0, SFS=0**

The study team decided to add an additional analysis to summarize the symptomatic remission rate to investigate how symptoms improve over the study duration.

Statistical Analysis Plan

Sponsor Name: Bridge Biotherapeutics, Inc.
Sponsor Protocol ID: BBT401-UC-005

- **Change from baseline to Day 57 in the partial Mayo score**

The study team decided to also present the change from baseline to Day 57 in the partial Mayo score to better evaluate the effects of BBT-401-1S.

8. Data Issues

No known data issues at the time of preparing this SAP.

9. References

- 1 CPMP. Points to Consider on Missing Data. EMEA: London, 2001. Available at https://www.ema.europa.eu/en/documents/scientific-guideline/points-consider-missing-data_en.pdf
- 2 ICH. *ICH E3 Guideline: Structure and Content of Clinical Study Reports Questions & Answers*, 2012. Available at http://www.ich.org/fileadmin/Public_Web_Site/ICH_Products/Guidelines/Efficacy/E3/E3_QAs_R1_Step4.pdf

Appendix 1: Document History

Document Version, Status, Date	Summary/Reason for Changes
Version XXX, DDMMYYYY	Not applicable; the first version

Appendix 2: Sample SAS Code for MMRM

[REDACTED]

[REDACTED]

[REDACTED]

[REDACTED]

Statistical Analysis Plan

Sponsor Name: Bridge Biotherapeutics, Inc.

Sponsor Protocol ID: BBT401-UC-005

[REDACTED]

[REDACTED]

[REDACTED]

CONFIDENTIAL

Page 30 of 30
